11.8 Safety Reporting for IND Holders

In accordance with 21 CFR 212.32, Sponsor-Investigator of the study conducted under an IND must comply with following safety-reporting requirements:

a. Expedited IND Safety Reports:

BrUOG will fax reports to the FDA for IND Safety Reports: [name], unless per the IND status BrUOG is to submit the SAEs to the Division Fax instead.

b. IND Annual Reports, for IND study only

If the FDA has granted an IND number, it is a requirement of 21 CFR 312.33, that an annual report is provided to the FDA within 60-days of the IND anniversary date. 21 CRF 312.33 provides the data elements that are to be submitted in the report. The Annual Report should be filed in the study's Regulatory Binder, and a copy provided to Novartis as a supporter of this study.

11.9 Adverse event updates/IND safety reports External

Novartis shall notify the Brown University Oncology Research Group (BrUOG) via an IND Safety Report of the following information:

- Any AE associated with the use of study drug in this study or in other studies that is both serious and unexpected.
- Any finding from tests in laboratory animals that suggests a significant risk for human subjects including reports of mutagenicity, teratogenicity, or carcinogenicity.

BrUOG will then notify the sites who shall notify their IRB/EC promptly of these new serious and unexpected AE(s) or significant risks to subjects.

12.0 REMOVAL OF PATIENTS FROM PROTOCOL THERAPY

Extraordinary medical circumstances or withdrawal of consent by the patient: If, at any time, the constraints of this protocol are detrimental to the patient's health, and/or the patient no longer wishes to continue protocol therapy, the patient shall be withdrawn from protocol therapy. Patients will also be withdrawn from study for the following reasons:

- 1. Disease Progression: Any patient with disease progression should be removed from study. Details and tumor measurements should be documented on flow sheets.
- 2. Patient is unable to tolerate the toxicity resulting from the study treatment, even with optimal supportive care, in the opinion of the Treating Physician. Adverse event(s) that, in the judgment of the investigator, may cause severe or permanent harm or which rule out continuation of study drug.
- 3. The physician feels it is in the best interest of the patient to stop the treatment.
- 4. Inter current illness that would, in the judgment of the Investigator, affect assessment of clinical status to a significant degree or require discontinuation of study treatment
- 5. Non protocol chemotherapy or immunotherapy is administered during the study
- 6. Noncompliance with protocol or treatment—major violation
- 7. Pregnancies or Suspected Pregnancies (including positive pregnancy test)
- 8. Patient is lost to follow-up
- 9. Patient refuses to continue treatment (patient will continue to be followed for disease-free survival and overall survival)
- 10. Death

In this event notify:

Brown University Oncology Research Group (BrUOG) Central Office, [contact] [contact]

The BrUOG Central Office will in turn notify the Principal Investigator.

*Document the reason(s) for withdrawal on flow sheets. Follow the patient for survival with followup forms as dictated by the protocol

13.0 FOLLOW-UP

All Subjects that discontinue treatment early for any reason (not including screen fails or patient with withdraw consent/decline study participation) as well as patients who complete therapy will be followed for survival (up to 5 years). At treatment discontinuation, subjects will undergo adverse event evaluation and again approximately 2 weeks and 30 days post the last treatment (radiation, capecitabine or study drug, whatever is the last date of treatment). In addition off study evaluations will be done when treatment is discontinued -Section 6.0.

14.0 REGULATORY CONSIDERATIONS

This research study is sponsored by the Principal Investigator, [name], in collaboration with Brown University Oncology Research Group (BrUOG), which will serve as the central coordinating office for the study. This study is supported by Novartis (the makers of BYL719).

14.1 Protection of Human Subjects

The Investigator must ensure that patients or their legally acceptable representatives are clearly and fully informed about the purpose, potential risks and other critical issues regarding clinical trials in which they volunteer to participate. Preparation of the consent form is the responsibility of the Investigator and must include all elements required by CFR 21 Part 50.25 and the local IRB.

14.2 Compliance with the Protocol and Protocol Revisions:

The study must be conducted as described in this approved protocol.

All revisions to the protocol must be provided to Brown University Oncology Research Group, and Novartis. The Investigator should not implement any deviation or change to the protocol without prior review and documented approval/favorable opinion from the IRB/IEC and Novartis of an Amendment, except where necessary to eliminate an immediate hazard(s) to study patients.

Documentation of approval signed by the chairperson or designee of the IRB(s)/IEC(s) must be sent to Brown University Oncology Research Group, and Novartis. If the revision is an Administrative Letter, Investigators must inform their IRB(s)/IEC(s).

The Investigator must ensure that patients or their legally acceptable representatives are clearly and fully informed about the purpose, potential risks and other critical issues regarding clinical trials in which they volunteer to participate. Preparation of the consent form is the responsibility of the Investigator and must include all elements required by CFR 21 Part 50.25 and the local IRB.

After the study has been fully explained, written informed consent will be obtained from either the patient or his/her guardian or legal representative prior to study participation. The method of obtaining and documenting the informed consent and the contents of the consent will comply with ICH-GCP and all applicable regulatory requirement(s).

14.3 Protocol amendments or changes in study conduct:

Any change or addition (excluding administrative) to this protocol requires a written protocol amendment that must be reviewed and approved and created by Brown University Oncology Research Group, who will obtain approval by Novartis and the investigator before implementation. Amendments significantly affecting the safety of subjects, the scope of the investigation or the scientific quality of the study require additional approval by the IRB at each study center. A copy of the written approval of the IRB must be provided to Brown University Oncology Research Group, and Novartis.

These requirements for approval should in no way prevent any immediate action from being taken by the investigator or by Brown University Oncology Research Group and Novartis in the interests of preserving the safety of all patients included in the trial. If an immediate change to the protocol is felt to be necessary by the investigator and is implemented for safety reasons Brown University Oncology Research Group and Novartis must be notified and the IRB at the center must be informed immediately. Amendments affecting only administrative aspects of the study do not require formal protocol amendments or IRB approval but the IRB must be kept informed of such administrative changes.

Examples of administrative changes not requiring formal protocol amendments include:

- Changes in the staff used to monitor trials (Novartis considers a change in Principal Investigator or the addition of sub-site(s) to be substantial and requires Novartis approval prior to implementation)
- Minor changes in the packaging or labeling of study drug.

15.0 DATA MONITORING / OUALITY ASSURANCE/ RECORD RETENTION

15.1 Good Clinical Practice: The study will be conducted in accordance with the International Conference on Harmonisation (ICH) for Good Clinical Practice (GCP) and in the US Code of Federal Regulations. The investigator will be thoroughly familiar with the appropriate use of the drug as described in the protocol and Investigator's Brochure. Essential clinical documents will be maintained to demonstrate the validity of the study and the integrity of the data collected. Master files should be established at the beginning of the study, maintained for the duration of the study and retained according to the appropriate regulations.

15.2 Patient Confidentiality: In order to maintain patient privacy, all data capture records, drug accountability records, study reports and communications will identify the patient by initials and the assigned patient number. The investigator will grant monitor(s) and auditor(s) from Novartis or its designees and regulatory authority (ies) access to the patient's original medical records for verification of data gathered on the data capture records and to audit the data collection process. The patient's confidentiality will be maintained and will not be made publicly available to the extent permitted by the applicable laws and regulations.

15.3 Protocol Compliance: The investigator will conduct the study in compliance with the protocol given approval/favorable opinion by the IRB/IEC and the appropriate regulatory authority(ies). Changes to the protocol will require approval from Novartis and written IRB/IEC approval/favorable opinion prior to implementation, except when the modification is needed to eliminate an immediate hazard(s) to

patients. The IRB/IEC may provide, if applicable regulatory authority (ies) permit, expedited review and approval/favorable opinion for minor change(s) in ongoing studies that have the approval /favorable opinion of the IRB/IEC. The investigator will submit all protocol modifications to Novartis and the regulatory authority (ies) in accordance with the governing regulations.

Any departures from the protocol must be fully documented in the source documents.

15.4 On-site Audits: Regulatory authorities, the IEC/IRB and/or Novartis clinical quality assurance group may request access to all source documents, data capture records, and other study documentation for on-site audit or inspection. Direct access to these documents must be guaranteed by the investigator, who must provide support at all times for these activities.

15.5 Drug Accountability: Accountability for the drug at all study sites is the responsibility of the principal investigator. The investigator will ensure that the drug is used only in accordance with this protocol. Drug accountability records indicating the drug's delivery date to the site (if applicable), inventory at the site (if applicable), use by each patient, and return to BrUOG prior to approval for disposal of the drug (if applicable and if approved by Novartis) will be maintained by the clinical site. Accountability records will include dates, quantities, lot numbers, expiration dates (if applicable), and patient numbers.

All material containing BYL719 ® will be treated and disposed of as hazardous waste in accordance with governing regulations.

15.6 Premature Closure of the Study: This study may be prematurely terminated, if in the opinion of the investigator or Novartis, there is sufficient reasonable cause. Written notification documenting the reason for study termination will be provided to the investigator or Novartis by the terminating party.

Circumstances that may warrant termination include, but are not limited to:

- Determination of unexpected, significant, or unacceptable risk to patients
- Failure to enter patients at an acceptable rate
- Insufficient adherence to protocol requirements
- Insufficient complete and/or evaluable data
- Plans to modify, suspend or discontinue the development of the drug
- Should the study be closed prematurely, all study materials must be returned to Novartis.

15.7 Record Retention:

The investigator will maintain all study records according to ICH-GCP and applicable regulatory requirement(s).

The Brown University Oncology Research Group, as coordinator of this study, is responsible for ensuring proper conduct of the study with regard to protocol adherence and the validity of the data recorded on the case report forms. The Principle Investigator ([name].) and Brown University Oncology Research Group Manager of Operations ([name]) will monitor this study. The case report forms will be monitored against the submitted documents for accuracy, completeness, adherence to the protocol and regulatory compliance.

U.S. FDA regulations (21CFR312.62[c] require all records and documents pertaining to the conduct of this study and the distribution of investigational drug, including CRFs, consents forms, laboratory test results and medication inventory records, must be retained by the Principal Investigator for 2 years after marketing application approval. If no application is filed, these records must be kept 2 years after the investigation is discontinued and the FDA and the applicable local health authorities are notified. Amgen will notify the Principle Investigator if an application is filed.

16.0 DATA SAFETY AND MONITORING BOARDS

All trials initiated by the Brown University Oncology Research Group (BrUOG) are subject to oversight by the Data Safety Monitoring Board (DSMB). This board meets two times per year with any additional meetings scheduled when needed. The responsibilities are as follows:

- Familiarize themselves with the research protocol (s)
- The DSMB reviews trial performance information such as accrual information.
- Review interim analyses of outcome data and cumulative toxicity data summaries to determine
 whether the trial should continue as originally designed, should be changed, or should be
 terminated based on these data.
- The DSMB also determines whether and to whom outcome results should be released prior to the reporting of study results.
- All adverse events are reviewed by the committee, with assurances that these have been in fact sent for review to all pertinent IRBs.
- Review of reports of related studies to determine whether the monitored study needs to be changed or terminated.
- Review major proposed modifications to the study prior to their implementation (e.g., termination, dropping an arm based on toxicity results or other reported trial outcomes, increasing target sample size).
- Following each DSMB meeting, provide the study leadership with written information concerning findings for the trial as a whole related to cumulative toxicities observed and any relevant recommendations related to continuing, changing, or terminating the trial.

The study leadership will provide information on cumulative toxicities and relevant recommendations to the local principal investigators to be shared with their IRB's.

17.0 STATISTICS

Sample Size Justification:

Three patients will be accrued to level 1. If no dose limiting toxicities are observed following completion of BYL719, capecitabine and radiation, and once the 2 week post treatment completion assessment is performed, then accrual to level 2 will proceed. If a DLT is observed in one of the first 3 patients in a dose level, then accrual for that level will be expanded to 6 patients. Two or more instances of DLT in a cohort of 6 patients will result in the preceding dose level being defined as the MTD. After determination of the MTD, the final cohort will be expanded to treat a total of 24 patients on the entire study. During the dose escalation phase, if 3 or more patients have a DLT or there is one grade 5 treatment-related serious adverse event that occurs, protocol accrual will be suspended. If this circumstance occurs, the Brown University Oncology Research Group data safety monitoring Chair will review the adverse event data and make

appropriate recommendations to the Brown University Oncology Research Group and the FDA about the study. Sample size: Approximately 24.

Threshold To Bring BYL719 Forward With Capecitabine and Radiation in Rectal Cancer: The primary goal of this Brown University Oncology Research Group is to determine that a safe dose of BYL719 can be administered with capecitabine and radiation in patients with rectal cancer. *Therefore, the threshold of success for this phase I study is to establish safety.* In a subsequent NRG study, within the TNT framework, a randomized phase II study will be planned exclusively in patients with PIK3CA mutations to assess whether pathologic complete response is improved within this specific subgroup of patients.

A patient will be considered inevaluable if they receive <67% of their total intended treatment (BYL719, Capecitabine or Radiation) for non-protocol required reasons.

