4.0 TREATMENT

4.1 Treatment:

This is a phase I dose escalation study adding BYL719 to standard capecitabine and radiation.

Capecitabine: 825mg/m²/BID Sunday night through Friday morning on radiation days (See appendix H for capecitabine dosage per BSA)

Dosing: Sunday evening –Friday morning (the night before to the morning of each chemo treatment, not Monday AM-Friday PM): Dose 1 to be taken Sunday PM, then Monday –Thursday AM/PM dosing, then last dose Friday AM.

Radiation: 50.4 Gy, 180 cGY/fraction x 28 fractions:

BYL 719: BYL719 will be given once daily po, from Day 1 of radiation to the final treatment with radiation. BYL719 will be administered orally once daily on a continuous dosing schedule and dosed on a flat-fixed dose and not adjusted by body weight or body surface area.

Missed doses of BYL 719 are not made up and BYL719 will be stopped when radiation is completed.

IF RADIATION IS NOT GIVEN SECONDARY TO TOXICITY OR TOXICITY RECOVERY (OR PER PROTOCOL) ETC, THEN PATIENT IS TO BE INSTRUCTED TO NOT TAKE CAPECITABINE OR BYL719 DRUGS. IF RADIATION IS NOT GIVEN SECONDARY TO A HOLIDAY OR AN ADMINISTRATIVE REASON (MACHINE IS DOWN, SNOW STORM, SCHEDULING ETC) THEN CAPECITABINE IS TO BE HELD (ONCE IT IS KNOWN TREATMENT WON'T BE GIVEN, AS DRUG IS TO BE GIVEN WITH RADIATION). BYL719 HOWEVER, IS STILL TO BE GIVEN AS TREATMENT IS ON A CONTINUOUS BASIS AND REASON IS NOT FOR TOXICITY (BUT MUST BE STOPPED ONCE RADIATION ENDS).

Surgery will be performed approximately 6-10 weeks after the last treatment of BYL719/capecitabine + Radiation

No of pts	Dose Level*	Cohort Level*	Capecitabine	Radiation.
3-6	1	BYL719 200 mg/day	Capecitabine, 825mg/m2 BID Sunday PM-Fri AM	50.4 GY RT
3-6	2	BYL 719 250 mg/day	Capecitabine, 825mg/m2 BID Sunday PM-Fri AM	50.4 GY RT
3-6	3	BYL 719 300 mg/day	Capecitabine, 825mg/m2 BID Sunday PM-Fri AM	50.4 GY RT

(Dose Level -1: 150mg/day, to be used if dose level 1 is not tolerated based on DLTs or in the case when a dose reduction may be needed for a patient on dose level 1.

Only 1 dose reduction is permitted per patient for criteria noted in section 5)

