Three patients will be accrued to level 1. If dose level 1 is not tolerated then dose level -1 will be investigated. If no dose limiting toxicities are observed following completion of BYL719, capecitabine and radiation, and after patients are observed for 2 weeks post completion, then accrual to level 2 will proceed. If a DLT is observed in one of the first 3 patients in a dose level, then accrual for that level will be expanded to 6 patients. Two or more instances of DLT in a cohort of 6 patients will result in the preceding dose level being defined as the MTD. After determination of the MTD, the final cohort will be expanded so that a total of 24 patients are treated on study. A patient will be considered inevaluable if they receive <67% of their total intended treatment (BYL719, Capecitabine or Radiation) for non-protocol required reasons.

During the MTD dose finding portion, patients who are removed from study for reasons other than a DLT, defined in section 5.2, will be replaced.

If a dose limiting toxicity occurs, BYL719 will be held until the toxicity reduces to \leq grade 1 at which point patients will be permanently dose reduced by 1 dose level. Patients may continue to receive their capecitabine and radiation as per institutional standard of care when toxicities resolve to \leq grade 2.

If treatment is held for more than 28 days, then patient should come off study. Definition of Dose Limiting Toxicities

- Grade 4 neutropenia (ANC < 500/mm³)
- ANC $<1000/\text{mm}^3$ with fever (temp > 101) or infection
- Grade 4 thrombocytopenia: Platelets <25,000/mm³
- Platelets <50,000/mm³ requiring transfusion
- Grade 3 or 4 treatment related non-hematologic toxicities excluding alopecia. Grade 3 nausea, vomiting or diarrhea will only be considered a dose limiting toxicity if it occurs for greater than 48 hours despite maximal medical support. Grade 3 electrolyte abnormalities will not be considered dose limiting toxicities if the electrolyte disorder can be corrected to grade 2 or less within 72 hours. A grade 4 electrolyte abnormality will be considered a DLT.
- Patients who receive < 67% of intended BYL719 or capecitabine secondary to treatment related toxicities will also be considered as having a DLT (patients will be considered inevaluable)

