5.2 Definition of Dose Limiting Toxicities

- Grade 4 neutropenia (ANC < 500/mm³)
- ANC $<1000/\text{mm}^3$ with fever (temp > 101) or infection
- Grade 4 thrombocytopenia: Platelets <25,000/mm³
- Platelets <50,000/mm³ requiring transfusion
- Grade 3 or 4 treatment related non-hematologic toxicities excluding alopecia. Grade 3 nausea, vomiting or diarrhea will only be considered a dose limiting toxicity if it occurs for greater than 48 hours despite maximal medical support. Grade 3 electrolyte abnormalities will not be considered dose limiting toxicities if the electrolyte disorder can be corrected to grade 2 or less within 72 hours. A grade 4 electrolyte abnormality will be considered a DLT.
- Patients who receive < 67% of intended BYL719 or capecitabine secondary to treatment related toxicities will also be considered as having a DLT

During the MTD dose finding portion, patients who are removed from study for reasons other than a DLT, defined in section 5.2, will be replaced.

5.3 Management of Specific Toxicities are outlined below for all patients: most conservative assessments must be used for management and modification:

If a dose limiting toxicity occurs, BYL719 will be held until the toxicity reduces to \leq grade 1 at which point patients will be permanently dose reduced by 1 dose level. Patients may continue to receive their capecitabine and radiation as per institutional standard of care when toxicities resolve to \leq grade 2.

If treatment is held for more than 28 days, then patient should come off study.

During the MTD dose finding portion, patients who are removed from study for reasons other than a DLT, defined in section 5.2, will be replaced.

For toxicities other than dose limiting toxicities, specific dose adjustments, based on the worst preceding toxicity as graded by the NCI Clinical Toxicity Criteria ([NCI-CTCAE version 4.03]), are described below. A maximum of 1 dose reduction of BYL719 from the starting dose may be allowed.

Missed doses of BYL 719 are not made up and BYL719 will be stopped when radiation is completed.

Dose Modifications for BYL719 (TREATMENT RELATED (BYL719)): This table only applies once patient has begun treatment on study and it is only applicable while they are receiving treatment on study		
Worst toxicity (CTCAE 4.03 Grade)	Dose Modifications for BYL719	
HEMATOLOGICAL		
Neutropenia (ANC)		
Grade 3 (ANC < 1.0 - 0.5 x 10 ⁹ /L)	Omit dose until resolved to ≤ Grade 1, then:	

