All other AEs not noted above (T	reatment Related to BYL719):	
All other AEs (this pertains to no	n-lab AEs only)	
Grade 1 or 2	Maintain dose level	
Grade 3	Omit dose until resolved to ≤ Grade 1, then reduce BYL719 by 1 dose level	
	Note: Omit dose for \geq Grade 3 vomiting or \geq Grade 3 nausea only if the vomiting or nausea cannot be controlled with optimal antiemetic treatment as per local practice.	
Grade 4	Permanently discontinue patient from BYL719	
	Note: Omit dose for \geq Grade 3 vomiting or \geq Grade 3 nausea only if the vomiting or nausea cannot be controlled with optimal antiemetic treatment as per local practice.	

Management of Pneumonitis in patients receiving BYL719

All patients will be routinely asked about and observed for the occurrence of adverse events including new or changed pulmonary symptoms (consistent with lung abnormalities). Patients who are suspected to have 2/15/15, 2/19/15, 3/20/15, 3/27/15,4/23/15, 6/11/15, 6/11/15, 8/14/15, 8/17/15, 8/26/15, 8/31/15, 9/3/15, 9/8/15 approved Novartis, 29 2/11/15, 2/14/15,

9/11/15, 9/14/15, 9/21/15, RNEXECPI 9/29/15, 10/5/15 novartis, 10/6/15 approved Novartis, 10/8/15, 10/19/12 sent FDA, 11/4/15 clinical hold, 11/5/15 sent Novartis, SMP 11/6/15, 11/20/20/15, Amendment # 1 5/6/16, Amendment # 2 6/2/16, Amendment # 3 10/31/16 –FDA Reviewer edits, Amendment #3 updated 1/19/2017, Amendment # 4 6/20/17, Amendment # 5 8/9/2017 with IB 10, AMENDMENT #6 1/16/18

developed pneumonitis should suspend study treatment with BYL719 (alpelisib) immediately and undergo appropriate imaging (high resolution CT scan); and broncho-alveolar lavage and biopsy should be considered if clinically appropriate. Infectious causes of interstitial lung disease should be ruled out. Investigators should follow institutional practice for management of pneumonitis which generally includes treatment with high dose corticosteroids; antibiotic therapy should be administered concurrently if infectious causes are suspected. Consultation with a pulmonologist is highly recommended for any pneumonitis case during the study treatment. BYL719 (alpelisib), capecitabine and radiation (if suspected to be etiologically related to the AE of pneumonitis) should be permanently discontinued in all patients with confirmed pneumonitis.

Consultation with a pulmonologist is highly recommended for any pneumonitis case during the study treatment.

If the pneumonitis is confirmed to be study drug related, BYL719 must be discontinued.

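### The MTD stop counts instances of DLT while the neighbouring rules count patients, so read literally one patient can fail a dose level

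*Combined protocol and SAP*

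**What the plan says.** The rule that fixes the MTD, the only primary objective, stands in the same words in Sections 4.1 and 17: "Two or more instances of DLT in a cohort of 6 patients will result in the preceding dose level being defined as the MTD". In Section 17 the rules around it use a different unit. The expansion trigger begins "If a DLT is observed in one of the first 3 patients in a dose level", and accrual is suspended during escalation "if 3 or more patients have a DLT or there is one grade 5 treatment-related serious adverse event that occurs". Once the MTD is set, "After determination of the MTD, the final cohort will be expanded to treat a total of 24 patients on the entire study".

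The DLT list appears twice, in Sections 4.1 and 5.2. Its last item concerns lost treatment: "Patients who receive < 67% of intended BYL719 or capecitabine secondary to treatment related toxicities will also be considered as having a DLT". Section 4.1 adds in brackets that such patients are inevaluable; Section 5.2 does not. In both lists the non-hematologic item names grades 3 and 4 only. During dose finding, a patient removed for a reason other than a DLT is replaced.

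On exposure, "BYL719 will be given once daily po, from Day 1 of radiation to the final treatment with radiation". After a DLT the drug is held until recovery, "at which point patients will be permanently dose reduced by 1 dose level". Some rows of the Section 5.3 dose-modification table end the drug instead. For grade 4 non-laboratory events not listed elsewhere, the row reads "Permanently discontinue patient from BYL719".

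**The concern.** A decision rule for a primary endpoint should give one answer for one set of data, and this one can give two. Take a level with six patients, one of whom has a DLT. Counted by patients, the level passes. Counted by instances, it fails if that patient's course meets two items on the DLT list. The level below then becomes the MTD and receives the expansion cohort, and no higher level is tried. If the failing level is level 1, Section 4.1 sends the trial to level -1.

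Counting instances therefore errs toward a lower MTD. Two neighbouring ambiguities about who enters the count work the other way. A patient with a toxicity-driven DLT who is set aside as inevaluable, or a treatment-related death that matches no DLT item, would lower the tally and could leave the MTD too high.

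**Working it through.** **No figure to reproduce.** The plan gives no target DLT rate or operating characteristics for the rule. The rates below are assumptions shown over a range.

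**Can one patient supply two instances?**
- Section 4.1 gives 28 daily fractions, and BYL719 runs every day from the first to the last. With weekday fractions, a Monday or Tuesday start (Section 4.3) and no breaks, the course spans 38 calendar days.
- 25/38 = 65.8%, below 67%. 26/38 = 68.4%, above it. Thirteen or more lost doses therefore meet the lost-treatment item.
- A patient with a treatment-related DLT that permanently ends BYL719 by about day 25 meets the toxicity item and the lost-treatment item. No rechallenge is needed.
- One qualification concerns grade 4 events. The general rule is to hold and then reduce after a DLT, and Section 5.3 introduces its table as being for other toxicities. Yet the table marks some rows as DLTs and ends the drug for others. Those passages need reconciling. The example needs only that some DLTs end the drug, which Section 12 also allows when toxicity cannot be tolerated.

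**How much does the unit matter?** Let p be the true DLT rate at a level and q the chance that a DLT patient supplies a second instance. Assume that patients are independent, that a level passes on 0 of 3 or on 1 of 3 followed by 0 of 3 (implied rather than stated for 1 of 6), and that 2 or 3 of the first 3 is a failure.

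- By patients: P(fail) = 1 − [(1−p)³ + 3p(1−p)⁵]
- By instances: P(fail) = 1 − [(1−p)³ + 3p(1−q)(1−p)⁵]

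At p = 0.20, (0.8)³ = 0.512 and 3(0.2)(0.8)⁵ = 0.1966. By patients, 1 − 0.7086 = 0.291. With q = 0.5, 1 − (0.512 + 0.0983) = 0.390.

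| True DLT rate | By patients | Instances, q = 0.1 | q = 0.5 | q = 1 (outer limit) |
|---|---|---|---|---|
| 10% | 9.4% | 11.2% | 18.2% | 27.1% |
| 20% | 29.1% | 31.1% | 39.0% | 48.8% |

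**Who enters the count?** Two sets of passages disagree or leave a gap.
- *Toxicity-driven under-67% patients.* Section 4.1 calls them both DLT and inevaluable; Section 5.2 calls them DLT only. Elsewhere, Sections 4.1 and 17 use inevaluable for treatment lost for reasons the protocol did not require, which is a different group.
- *Treatment-related death.* Grade 5 appears only as a suspension trigger. An early death would probably be caught by the lost-treatment item. A death after at least 67% of dosing, with no earlier listed DLT, matches no item, and suspending accrual does not add it to the tally.

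**The case against.** The strongest reply is that the intent is plain. The adjacent rules count patients, and the lost-treatment item can be read as classifying a patient rather than adding a second event. That is fair, and it makes this a wording inconsistency rather than a flawed design. The literal text still allows the other reading, and no sentence says that a patient counts once. The values of q have no support in the documents either, so the 31% to 39% shows sensitivity and is not a prediction.

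Three stronger readings are tempting.

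*Any 13-day hold creates a second instance.* The documents do not support this. Capecitabine and radiation resume after a DLT only once toxicity falls to grade 2 or below, so radiation may pause and the course lengthen. With a one-week pause and a 13-day hold, 45 − 13 = 32 doses are given: 32/38 = 84% or 32/45 = 71%, neither below 67%. The rechallenge route is also uncertain, because the second event occurs at the reduced dose and the plan does not say which level it counts against.

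*A toxic death goes unnoticed.* It does not. One treatment-related grade 5 event during escalation suspends accrual and goes to the data safety monitoring Chair, and the DSMB reviews all adverse events. Nor is it clear that a patient who dies after completing therapy counts as removed and so is replaced.

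*Declaring the MTD on 0 of 3 is an error.* The dose table plans 3 to 6 patients per level, so this is a design choice. The one-sided 95% upper bound is 63% for 0/3, but it is still 58% for 1/6, which a six-patient requirement would accept (39% for 0/6). On five assumed DLT curves, from 10/15/25% to 35/45/55% at levels 1 to 3, filling a three-patient MTD at level 1 or 2 to six would change the MTD in about 2% to 8% of trials. With no target rate stated, those changes cannot all be called corrections.

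**Conclusion.** The concern holds as a wording fault in the rule for the primary endpoint. Sections 4.1 and 17 should count patients; as written, one patient can fail a level that has one DLT patient in six. The size depends on an unknown share of DLT patients with a second instance. If that share is 10% to 50%, failure rises by about 2 to 10 percentage points at a 20% DLT rate (29.1% to between 31.1% and 39.0%) and by about 2 to 9 points at a 10% rate. If investigators already read the rule as patients, the practical effect is nil, but the text should say so.

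The conflict over inevaluable patients is direct and bears on the same count. The grade 5 gap is real but narrow: it concerns the tally, not oversight. Requiring six patients at the candidate level is a preference that the sponsor may weigh; it is not part of this finding.

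**What to change.** 1. In Sections 4.1 and 17, replace instances of DLT with *patients with a DLT*, and state that a patient who meets more than one DLT item counts once.
2. Word the stop as two or more such patients in a cohort of three or six. The text now gives no action for two among the first three. Filling that cohort to six could not bring it back under two, so the MTD is unchanged.
3. Make the DLT lists in Sections 4.1 and 5.2 agree on whether patients under 67% because of toxicity are evaluable for the MTD count.
4. Align the DLT list, the replacement rule and the grade 5 suspension rule so that a treatment-related death during dose finding is not left out of the MTD count.

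All four are text changes in one amendment, with no added patients, visits or delay.

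If the sponsor chooses to fill the candidate level to six, that does have a cost. On the assumed curves it takes about 2.4 expansion slots on average (from 13.0–14.9 to 10.6–12.6, level 3 included). Those slots close to stage IV patients, who are eligible only in the expansion. Each fill also adds accrual time plus about 7.5 weeks (5.5 of treatment and 2 of observation).
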